16.3 Analysis Plan

16.31 Primary Outcome Analyses:

- 16.311 Definition: The primary endpoint in the phase II portion of this trial is the proportion of complete plus very good partial responses after 4 cycles of induction treatment. A success is defined as an sCR, CR, or VGPR noted as the objective status on two consecutive evaluations. Response will be evaluated using the first 4 cycles of induction therapy. All patients meeting the eligibility criteria who have signed a consent form and have begun treatment will be evaluable for response, with the exception of patients who are determined to be a major violation.
- 16.312 Estimation: The proportion of successes will be estimated by the number of successes divided by the total number of evaluable patients.

Confidence intervals for the true success proportion will be calculated according to the approach of Duffy and Santner (Duffy D 1987).

16.32 Secondary Outcome Analyses

- 16.321 The \geq PR response rate after 4 cycles of induction treatment with pembrolizumab added to lenalidomide and dexamethasone will be estimated by the number of patients who achieve a PR, VGPR, CR, or sCR after 4 cycles divided by the total number of evaluable patients. Exact binomial 95% confidence intervals for the true success rate will be calculated.
- 16.322 The \geq VGPR response rate at any time during treatment with pembrolizumab added to lenalidomide and dexamethasone will be estimated by the number of patients who achieve a VGPR, CR, or sCR at any time divided by the total number of evaluable patients. Exact binomial 95% confidence intervals for the true success rate will be calculated.
- 16.323 Survival time is defined as the time from registration to death due to any cause. The distribution of survival time will be estimated using the method of Kaplan-Meier⁷.
- 16.324 Progression-free survival is defined as the time from registration to the earliest date of documentation of disease progression or death due to any cause. Patients who receive subsequent treatment for myeloma before disease progression will be censored on the date of their last disease assessment prior to initiation of the subsequent treatment. Transplant will not be considered subsequent treatment. The distribution of progression-free survival will be estimated using the method of Kaplan-Meier
- 16.325 Adverse Events: All eligible patients that have initiated treatment will be considered evaluable for assessing adverse event rate(s). The maximum grade for each type of adverse event will be recorded for each patient, and frequency tables will be reviewed to determine patterns. Additionally, the relationship of the adverse event(s) to the study treatment will be taken into consideration.
- 16.326 The success rate of stem cell collection following initial therapy with the combination of pembrolizumab, lenalidomide and dexamethasone in patients with newly diagnosed MM will be estimated by the number of patients with a successful stem cell collection divided by the total number of evaluable patients. Exact binomial 95% confidence intervals for the true success rate will be calculated.

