2.2 Secondary

2.21. To determine the \geq partial response (PR) rate after 4 cycles of treatment with Pembrolizumab added to standard doses of lenalidomide and dexamethasone.

2.22 To determine the \geq VGPR response rate at any time during treatment with Pembrolizumab added to standard doses of lenalidomide and dexamethasone.

2.23 To determine the progression free survival and overall survival among patients with previously untreated symptomatic MM following treatment with the combination of pembrolizumab, lenalidomide and dexamethasone.

2.24 To determine the toxicities associated with pembrolizumab added to standard doses of lenalidomide and dexamethasone in patients with previously untreated symptomatic MM.

2.25 To determine the success rate of stem cell collection following initial therapy with the combination of pembrolizumab, lenalidomide and dexamethasone in patients with newly diagnosed MM.

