- 3.28 Major surgery ≤ 14 days prior to study registration.
- 3.29a Radiotherapy ≤ 14 days prior to registration.
NOTE: If the involved field is small, 7 days will be considered a sufficient interval between treatment and administration of study drugs
- 3.29b Participation in any other clinical trials with other investigational agents not included in this trial, ≤ 21 days prior to registration
- 3.29c Active autoimmune disease that has required systemic treatment in the past 2 years (i.e. with use of disease modifying agents, corticosteroids or immunosuppressive drugs).
NOTE: Replacement therapy (eg., thyroxine, insulin, or physiologic corticosteroid replacement therapy for adrenal or pituitary insufficiency, etc.) is not considered a form of systemic treatment.
- 3.29d Has a history of (non-infectious) pneumonitis that required steroids or current pneumonitis.
- 3.29e Active infection requiring systemic therapy.
- 3.29f History or current evidence of any condition, therapy, or laboratory abnormality that might confound the results of the trial, interfere with the subject's participation for the full duration of the trial, or is not in the best interest of the subject to participate, in the opinion of the treating investigator.
- 3.29g Known psychiatric or substance abuse disorders that would interfere with cooperation with the requirements of the trial.
- 3.29h Is pregnant or breastfeeding, or expecting to conceive or father children within the projected duration of the trial, starting with the pre-screening or screening visit through 120 days after the last dose of trial treatment.
- 3.29i Received prior therapy with an anti-PD-1, anti-PD-L1, or anti-PD-L2 agent.
- 3.29j Known history of Human Immunodeficiency Virus (HIV) (HIV 1/2 antibodies).
- 3.29k Known active Hepatitis B (e.g., HBsAg reactive) or Hepatitis C (e.g., HCV RNA [qualitative] is detected).
- 3.29l Received a live vaccine ≤ 30 days of planned start of study therapy.

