13.8 Patient Ineligible

A patient is deemed *ineligible* if after registration, it is determined that at the time of registration, the patient did not satisfy each and every eligibility criteria for study entry. The patient may continue treatment off-protocol at the discretion of the physician as long as there are no safety concerns, and the patient was properly registered. The patient will go directly to the event-monitoring phase of the study (or off study, if applicable).

- If the patient received treatment, all data up until the point of confirmation of ineligibility must be submitted. Event monitoring will be required per Section 18.0 of the protocol.
- If the patient never received treatment, on-study material and the End of Active Treatment/Cancel Notification Form must be submitted. No further data submission is necessary.

13.9a Patient major violation

A patient is deemed a *major violation*, if protocol requirements regarding treatment in cycle 1 of the initial therapy are severely violated that evaluability for primary end point is questionable. All data up until the point of confirmation of a major violation must be submitted. The patient will go directly to the event-monitoring phase of the study. The patient may continue treatment off-protocol at the discretion of the physician as long as there are no safety concerns, and the patient was properly registered. Event monitoring will be required per Section 18.0 of the protocol.

13.9b Patient cancel

A patient is deemed a *cancel* if he/she is removed from the study for any reason before any study treatment is given. On-study material and the End of Active Treatment/Cancel Notification Form must be submitted. No further data submission is necessary.

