- c) Excretion – The systemic clearance of pembrolizumab is ~0.22 L/day and the terminal elimination half-life ($t_{1/2}$) is estimated to be ~26 days.
- d) Metabolism - Pembrolizumab is catabolized by general protein degradation processes; typical small molecule metabolic pathways (eg, cytochrome P450 enzymes, glucuronosyltransferases) do not contribute to its clearance.

15.16 **Potential Drug Interactions:** There are no known significant drug interactions.

15.17 **Known potential toxicities:**

Common known potential toxicities, > 10%:

Dermatologic: Pruritus, skin rash
 Gastrointestinal: diarrhea
 Neuromuscular & skeletal: arthralgia, back pain
 Respiratory: Cough

Less common known potential toxicities, 1% - 10%:

Infusion related reactions
 Dermatologic: vitiligo, severe skin reactions
 Endocrine & metabolic: Hypothyroidism, hyperthyroidism, hyponatremia
 Gastrointestinal: Colitis, abdominal pain
 Respiratory: Pneumonitis

Rare known potential toxicities, <1% (Limited to important or life-threatening):

Secondary adrenocortical insufficiency (immune-mediated), hepatitis (including autoimmune hepatitis), hypophysitis, nephritis, Guillain-Barre syndrome (immune-mediated), myositis (immune-mediated), pancreatitis (immune-mediated), uveitis (immune-mediated), and Type 1 diabetes mellitus.

Stevens-Johnson syndrome, Toxic Epidermal Necrolysis, and Immune-mediated myocarditis

Two important potential risks have been identified, although the data available thus far for these events does not provide sufficient evidence of a causal relationship to pembrolizumab. The two important potential risks are: a) myasthenic syndrome, and b) an increased risk of severe complications (such as early severe graft versus host disease and venoocclusive disease) of allogeneic transplant in patients with hematologic malignancies who have previously been treated with PD-1 inhibitors. The Sponsor continues to monitor and collect data on these potential risks in order to further characterize their potential relationship to Pembrolizumab.

15.18 **Drug procurement:** Pembrolizumab will be provided free of charge to study participants by Merck.

15.19 **Nursing Guidelines:**

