16.0 Statistical Considerations and Methodology

16.1 Overview

This is a phase II study of a novel regimen of pembrolizumab with lenalidomide and dexamethasone for initial treatment of newly diagnosed multiple myeloma patients requiring therapy. This study is designed to assess the VGPR or better response rate associated with therapy with pembrolizumab added to standard doses of lenalidomide and dexamethasone, in patients with previously untreated multiple myeloma using a single stage phase II study design with an interim analysis.

- 16.11 **Endpoint:** The primary endpoint of the trial is the rate of complete or very good partial response after 4 cycles of induction treatment. A success will be defined as an sCR, CR, or VGPR noted as the objective status on two consecutive evaluations. Response will be evaluated using the first 4 cycles of induction therapy. Throughout Section 16.0, sCR, CR, or VGPR will be considered synonymous with “success” in the phase II portion, unless specified otherwise.
- 16.12 **Sample Size:** The single-stage study design with an interim analysis to be used is fully described below. A minimum of 13 and a maximum of 37 evaluable patients will be accrued in the phase II study unless undue toxicity is encountered. We anticipate accruing an additional 4 patients to account for ineligibility, cancellation, major treatment violation, or other reasons for a maximum of 41 patients.
- 16.13 **Accrual Rate and Study Duration:** The anticipated accrual rate is 2-3 evaluable multiple myeloma patients per month. At this rate, it will likely take about 1.5 years to enroll the patients. The maximum total study duration is expected to be approximately 2 years, or until the last patient accrued has been observed for at least 6 months.

16.2 Statistical Design:

16.21 Decision Rule:

A combination of lenalidomide plus dexamethasone, an oral regimen, is the mainstay therapy for newly diagnosed multiple myeloma. In a large multi-center study, 208 patients were evaluated for response to treatment with lenalidomide plus low dose dexamethasone.⁶ Forty-nine patients (24%) achieved a complete or very good partial response. An increase in the rate of complete plus very good partial response with the addition of pembrolizumab to lenalidomide plus dexamethasone would be of interest.

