Accrual will be temporarily suspended to this study if at any time we observe events considered at least possibly related to study treatment (i.e. an adverse event with attribute specified as “possible,” “probable,” or “definite”) that satisfy one of the following:

- if 5 or more patients in the first 15 treated patients experience a Grade 4 or higher non-hematologic adverse event at least possibly related to treatment.
- if after the first 15 patients have been treated, 40% of all patients experience a Grade 4 or higher non-hematologic adverse event at least possibly related to treatment.

We note that we will review grade 4 and 5 adverse events deemed “unrelated” or “unlikely to be related”, to verify their attribution and to monitor the emergence of a previously unrecognized treatment-related adverse event.

16.5 Results Reporting on ClinicalTrials.gov:

At study activation, this study will have been registered within the “ClinicalTrials.gov” website. The Primary and Secondary Endpoints along with other required information for this study will be reported on www.ClinicalTrials.gov. For purposes of timing of the Results Reporting, the initial estimated completion date for the Primary Endpoint of this study is 2 years after the study opens to accrual. The definition of “Primary Endpoint Completion Date” (PECD) for this study is at the time the last patient registered has been followed for at least 6 months.

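### Section 16.325 reports adverse-event rates for eligible treated patients only, so toxicity submitted under Section 13.8 for treated patients later found ineligible is left out of the rates

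*Combined protocol and SAP*

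**What the plan says.** Four parts of the combined protocol and SAP bear on this.

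- **Section 16.325 (adverse events).** "All eligible patients that have initiated treatment will be considered evaluable for assessing adverse event rate(s". The maximum grade of each type of event is recorded per patient and shown in frequency tables. Two conditions apply: the patient is eligible and has started treatment.
- **Section 13.8 (patient ineligible).** Ineligibility is a finding made after registration about the patient's status at registration. The section foresees that treatment may already have been given: "If the patient received treatment, all data up until the point of confirmation of ineligibility must be submitted".
- **Section 16.42 (adverse event stopping rules).** The first clause applies "if 5 or more patients in the first 15 treated patients experience a Grade 4 or higher non-hematologic adverse event". The second clause refers to all patients once 15 have been treated. Neither clause has an eligibility condition.
- **Section 16.311 (response population).** Eligible, consented patients who began treatment are evaluable, "with the exception of patients who are determined to be a major violation". Section 16.325 has no such exception, so an eligible patient with a major violation stays in the adverse-event rates.

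Toxicity is secondary goal 2.24: "To determine the toxicities associated with pembrolizumab added to standard doses of lenalidomide and dexamethasone". That goal goes on to name patients with previously untreated symptomatic myeloma. No section plans an additional all-treated safety table.

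**The concern.** Eligibility is a reasonable filter for a response question about a defined population. For toxicity the relevant fact is exposure, and a patient who received the drugs was exposed whether or not an entry criterion was missed. Because major violations stay in, ineligibility is the only ground on which Section 16.325 leaves out a treated patient, and the plan gives no reason for it.

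The exclusion can also be informative, because some entry criteria overlap with listed toxicities. Exclusion 3.29d reads "Has a history of (non-infectious) pneumonitis that required steroids or current pneumonitis", and Section 15.17 lists "Respiratory: Pneumonitis" among the less common toxicities of pembrolizumab. A treated patient later found to breach 3.29d who then had pneumonitis would be missing from both the numerator and the denominator of the pneumonitis rate.

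What is at stake is the accuracy of the rates for a stated secondary goal, which Section 16.5 commits to public reporting, in a trial of at most 41 patients. At that size, one excluded patient can hold the only case of an uncommon event.

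**Working it through.** **Inputs from the plan.** Section 16.12 gives 37 evaluable patients and "an additional 4 patients to account for ineligibility, cancellation, major treatment violation, or other reasons". The plan's total reproduces: 37 + 4 = 41. The plan gives no figure for the number of treated patients later found ineligible and no expected adverse-event rate.

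**Assumptions.** There are 37 eligible treated patients, with no major violations added. A further k patients are treated and later found ineligible. I take k = 1 to 4; at k = 0 nothing changes. The value k = 4 uses the whole reserve and is an upper bound, because the reserve also covers cancellations, who under Section 13.9b are never treated, and major violations, who stay in the Section 16.325 set if eligible. The event counts of 7 and 0 are illustrations.

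**Step 1: the rates.** Let e be the patients with the event among the 37 eligible, and j (0 to k) those among the k ineligible.

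- Reported rate under Section 16.325: e/37
- All-treated rate: (e + j)/(37 + k)

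| Reported | k | Lowest all-treated (j = 0) | Highest all-treated (j = k) | Change in points |
|---|---|---|---|---|
| 7/37 = 18.9% | 1 | 7/38 = 18.4% | 8/38 = 21.1% | -0.5 to +2.1 |
| 7/37 = 18.9% | 4 | 7/41 = 17.1% | 11/41 = 26.8% | -1.8 to +7.9 |
| 0/37 = 0% | 1 | 0/38 = 0% | 1/38 = 2.6% | 0 to +2.6 |
| 0/37 = 0% | 4 | 0/41 = 0% | 4/41 = 9.8% | 0 to +9.8 |

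The reported rate is too low if the excluded patients had the event and slightly too high if they did not.

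**Step 2: the chance that a toxicity disappears from the rates altogether.** Suppose each patient, eligible or not, has the same independent risk p. Given that at least one treated patient has the event, the probability that only ineligible patients have it is

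[1 - (1 - p)^k] × (1 - p)^37 / [1 - (1 - p)^(37 + k)]

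- p = 1%, k = 1: 0.0100 × 0.6894 / 0.3174 = 2.2%
- p = 1%, k = 4: 0.0394 × 0.6894 / 0.3377 = 8.0%
- p = 5%, k = 1: 0.0500 × 0.1499 / 0.8576 = 0.9%
- p = 5%, k = 4: 0.1855 × 0.1499 / 0.8779 = 3.2%

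Equal risk is itself an assumption. If the missed criterion marks susceptibility to the event, as in the pneumonitis example, the chance would be higher.

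**The case against.** The best case for leaving the text alone has four parts.

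- **The goal names a population.** Goal 2.24 concerns previously untreated symptomatic myeloma. A patient who breaches 3.11, 3.21 or 3.22 (for example, smoldering or previously treated disease) is outside it, and an eligible-only set then follows the goal. This stands for those breaches. It does not cover breaches such as 3.29d, where the patient has the disease the goal describes.
- **Nothing is lost from safety reporting.** This also stands. Section 10.5 records adverse events from consent to 30 days after treatment with no eligibility condition. Section 10.53 sends serious events in any subject to the sponsor and the manufacturer, and Section 10.8 requires Grade 3 and 4 events regardless of attribution. A reader might infer that toxicity in these patients goes unrecorded or unreported. Section 10 does not support that. It does not put the events into a rate, however.
- **Different populations for monitoring and reporting are not a contradiction.** An accrual rule cannot wait for eligibility findings made after registration, while a final table can. A reader might go further and set the count that paused accrual against a reported rate that looks lower. The documents do not support that comparison: Section 16.42 counts a composite (Grade 4 or higher, non-hematologic, at least possibly related), while Section 16.325 tabulates the maximum grade for each type of event and plans no such composite. The contrast shows only that the plan already uses a treated-patient basis for safety.
- **The number affected may be zero.** Section 6.13 has eligibility verified before registration is accepted. This stands and limits the size of the point.

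**Conclusion.** The point holds as a small, nearly free improvement. On its plain reading, Section 16.325 leaves treated patients later found ineligible out of the adverse-event rates, although Section 13.8 already requires their data, and no other planned table brings them in.

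The likely size is that of the one-patient case, or nothing. The four-patient figures are a ceiling, and all the figures rest on assumed values of k and of the event counts. A reader might infer that the plan understates toxicity. The documents do not support a fixed direction: the rate falls or rises according to whether the excluded patients had the event. The case for change rests on the exclusion being unexplained and possibly informative. The response design, its error rates and its sample size are unaffected.

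**What to change.** In Section 16.325, replace the opening phrase that limits the set to eligible patients who started treatment with: *All patients who received any study treatment*. State in the adverse-event tables how many of these patients were later found ineligible. Add a footnote that their data may stop at confirmation of ineligibility (Section 13.8), so their event counts are minimums.

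The cost is one phrase and one footnote. No new data, visits or patients are needed. If the sponsor also wants rates restricted to the population named in goal 2.24, an eligible-only column can be shown beside the all-treated one from the same data.

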16.33 Correlative Analyses (IRB#521-93)

- 16.331 PDL-1 expression on myeloma cells and non-tumor cell compartments from the bone marrow will be assessed at baseline. Each measure will be summarized descriptively by median, min, max and interquartile range.
- 16.332 Markers of T-cell activation and exhaustion will be summarized descriptively by median, min, max, and interquartile range at each time point. Patterns over time will be summarized by absolute difference or relative change. Changes across time will be assessed using paired

analyses, including Wilcoxon signed rank tests. Jitplots will be used to visually examine differences between groups for continuous factors.

16.333 NK cell function and numbers will be summarized descriptively by median, min, max, and interquartile range at each time point. Patterns over time will be summarized by absolute difference or relative change. Changes across time will be assessed using paired analyses, including Wilcoxon signed rank tests. Jitplots will be used to visually examine differences between groups for continuous factors.

16.34 Over Accrual: If more than the target number of patients are accrued, the additional patients will not be used to evaluate the stopping rule or used in any decision making processes; however, they will be included in final endpoint estimates and confidence intervals.

16.4 Data & Safety Monitoring:

16.41 The principal investigator(s) and the study statistician will review the study at least twice a year to identify accrual, adverse event, and any endpoint problems that might be developing. The Mayo Clinic Cancer Center (MCCC) Data Safety Monitoring Board (DSMB) is responsible for reviewing accrual and safety data for this trial at least twice a year, based on reports provided by the MCCC Statistical Office.

16.42 Adverse Event Stopping Rules: The stopping rules specified below are based on the knowledge available at study development. We note that the Adverse Event Stopping Rule may be adjusted in the event of either (1) the study re-opening to accrual or (2) at any time during the conduct of the trial and in consideration of newly acquired information regarding the adverse event profile of the treatment(s) under investigation. The study team may choose to suspend accrual because of unexpected adverse event profiles that have not crossed the specified rule below.

Accrual will be temporarily suspended to this study if at any time we observe events considered at least possibly related to study treatment (i.e. an adverse event with attribute specified as “possible,” “probable,” or “definite”) that satisfy one of the following:

- if 5 or more patients in the first 15 treated patients experience a Grade 4 or higher non-hematologic adverse event at least possibly related to treatment.
- if after the first 15 patients have been treated, 40% of all patients experience a Grade 4 or higher non-hematologic adverse event at least possibly related to treatment.

We note that we will review grade 4 and 5 adverse events deemed “unrelated” or “unlikely to be related”, to verify their attribution and to monitor the emergence of a previously unrecognized treatment-related adverse event.

16.5 Results Reporting on ClinicalTrials.gov:

At study activation, this study will have been registered within the “ClinicalTrials.gov” website. The Primary and Secondary Endpoints along with other required information for this study will be reported on www.ClinicalTrials.gov. For purposes of timing of the Results Reporting, the initial estimated completion date for the Primary Endpoint of this study is 2 years after the study opens to accrual. The definition of “Primary Endpoint Completion Date” (PECD) for this study is at the time the last patient registered has been followed for at least 6 months.

